10.3 Safety Assessments

Clariscan and any other GBCA used in this observational study are approved. Safety data will be collected, assessed and reported in accordance with post-marketing requirements. Clinical trial safety requirements do not apply.

[figure not shown]
The investigator(s) and the sponsor will review the safety data. The following safety data will be collected and evaluated:

AE collection for spontaneously reported AEs and serious AEs (SAEs) will begin at the time of contrast medium injected and continue up to 7 days after GBCA use for individual patient, unless consent is withdrawn. AEs reported in the first hour post-administration will be recorded as “immediate” and any AEs reported after 1 hour and up to 7 days will be recorded as “delayed”. Definition and examples of mild moderate and severe are mentioned in Section 15.2.

All AEs will be tabulated as number reported and percentage:

- 1 AEs, SAEs, severity of AEs, Clariscan vs GBCAs
- 2 AEs, SAEs, severity of AEs, Clariscan vs individual GBCA

Figure 4 Safety Profile

The radiological definition of ‘immediate’ and ‘delayed’ AEs and severity of AEs are in Section 15.2.

AE Definition: An AE is defined as any untoward medical occurrence in a patient or clinical investigation subject administered a pharmaceutical product and which does not necessarily have to have a causal relationship with this treatment. An AE can therefore be any unfavourable and unintended sign (including an abnormal laboratory finding), symptom, or disease temporally associated with the use of a study drug, whether or not considered related to that product. Only symptoms/signs that begin or worsen in severity and/or frequency after GBCA administration/use will be recorded as AEs in the eCRF.

The subjects will be closely observed and questioned with non-leading questioning (e.g., “How do you feel?”). The subjects will be instructed to immediately report any symptoms and signs to the study staff (i.e., between formal observations).

Both the investigator(s) and sponsor/CRO will perform a causality assessment on any AE, to assess whether or not there is a reasonable possibility (evidence to suggest) that the GBCAs caused the event.

Adverse Reaction: An AE that is caused by the GBCA.

Suspected Adverse Reaction: A reasonable possibility exists for causality between the GBCA and the AE.

10.3.1 Serious Adverse Events

An SAE is defined as any AE that:

- Results in death.
- Is life-threatening.
- Requires in-patient hospitalisation or prolongation of existing hospitalisation.
- Results in persistent or significant disability or incapacity.
- Is a congenital anomaly or birth defect.
- Is another important medical event.*

(*Other important medical events are those that may not result in death, be life threatening, or require hospitalisation, but may be considered an SAE when, based upon appropriate medical judgment, they may jeopardise the subject and may require medical intervention to prevent one of the outcomes listed above. Other Significant AEs are clinical laboratory abnormalities that qualify as AEs (other than those meeting the definition for serious) and any events that lead to an intervention (including premature discontinuation of GBCA, dose reduction or significant additional concomitant therapy), other than those reported as SAEs, will be reported and evaluated as other significant AEs.

10.3.2 Adverse Event and Serious Adverse Event Reporting

Study centres are instructed to report all AEs to GEHC Global Pharmacovigilance within 3 days by sending an email to [contact].

The centre may ask questions or notify Global Pharmacovigilance Drug Safety Surveillance (DSS) Oslo that an AE report has been sent by calling [contact] ([contact]) during office hours.

Individual case safety reports of valid serious and non-serious adverse drug reactions will be classified as solicited reports from post-marketing source. The Sponsor will report adverse drug reactions (i.e., AEs for which a causal relationship is at least a reasonable possibility) to health authorities in accordance with Regulation (EC) No. 726/2004 and Sponsor standard operating procedures (SOPs).

Causally unrelated reports of AEs will be summarised as part of any interim safety analysis and in the final study report, where applicable.

Adverse reactions to other medicines than Clariscan will be handled according to Global Pharmacovigilance SOP SPV.19.01 (Section 5.5).

Events which affect the known risk-benefit balance of Clariscan and/or impact on public health will be notified to competent authorities and the Agency, in accordance with Global Pharmacovigilance SOP SPV.19.19.

The centre should also notify the Medical Director of the SAE at one of the contact numbers below.

For any protocol or safety-related questions please contact the Medical Director:

[name] [name]
Senior Medical Advisor
Life Sciences
GE Healthcare
[name]
[name]
Spain
T :[name]
M [name]
[contact]

All AEs should be recorded using acceptable diagnoses, if possible. If an AE has already been reported it is not necessary to report each individual sign and symptom of that AE as a separate AE. For example, if myocardial infarction is reported as an AE, there is no need to report elevated creatine kinase and abnormal electrocardiogram, or other related signs, symptoms, or laboratory values as separate AEs. However, if both occurred in isolation and myocardial infarction was not diagnosed, then each event would be reported as an AE.

The intensity of all AEs will be graded as mild, moderate, or severe using the following definitions:

Mild:	Tolerable.
Moderate:	Interferes with normal activity.
Severe:	Incapacitating (causes inability to perform usual activity or work).

The investigator will be instructed to closely monitor each subject who experiences an AE (whether ascribed to the GBCA or not) until the outcome of the AE has been determined.

In addition to the investigator's own description of the AEs, each AE will be encoded by the sponsor/CRO according to a well-recognised dictionary of medical codes.

SAEs will be recorded in the eCRF if they occurred as follows:

- After a subject first received a GBCA and throughout the subject's follow-up period*, whether or not considered related to the GBCA, and
- After the subject's follow-up period, and for which a causal relationship to the GBCAs cannot be ruled out.

(*Follow-up period is defined as the protocol-stipulated period or, for subjects prematurely withdrawn from a study, the duration of a subject's participation.)

All serious and non-serious AEs must be followed for a final outcome until the end of the follow-up period. An outcome of "unknown" is not considered to be an acceptable final outcome. An outcome of "not yet resolved" is an acceptable final outcome for non-serious AEs at the end of a subject's participation in a study, and for SAEs at database lock.

10.4 Other Variables

10.4.1 Demographic Data

Subject date of birth, gender, height, weight, and BMI (calculated) will be collected.

10.4.2 Medical and Surgical History

- Medical history (including, in particular, history of allergy/asthma, eczema, renal, neurological)
- Number of previous MR, SPECT, PET, special x-ray examinations (e.g., fluoroscopy, barium studies) and CT examination for current illness/disease
- Major comorbidity and renal (level of renal impairment if know)/hepatic status
 - Renal impairment will be recorded as:

Every effort will be made to understand the stage of renal impairment based on estimated glomerular filtration rate (eGFR). The stages of chronic kidney disease (CKD) are classified as follows:

1. Stage 1: Kidney damage with normal or increased glomerular filtration rate (GFR; >90 mL/min/1.73 m²)
2. Stage 2: Mild reduction in GFR (60 to 89 mL/min/1.73 m²)

3. Stage 3a: Moderate reduction in GFR (45 to 59 mL/min/1.73 m²)
4. Stage 3b: Moderate reduction in GFR (30 to 44 mL/min/1.73 m²)
5. Stage 4: Severe reduction in GFR (15 to 29 mL/min/1.73 m²)
6. Stage 5: Kidney failure (GFR <15 mL/min/1.73 m² or dialysis)

Information regarding renal replacement therapy should be noted.

10.4.3 Concomitant and Concurrent Medication

Any medications taken by the subject within 24 hours of the MR examination through the end of the observation period will be recorded in the eCRF along with the indication. Either the generic or the trade name may be recorded.

10.4.4 Cumulative Data

To understand the Pattern of Use mentioned in Section 10.1, the following data will be complete only at the end of recruitment period:

- **Investigator Information (recorded once at the completion of recruitment):**

This information will be cumulative and consist of only numerical values and will include all procedures performed by the investigator regardless of whether or not the patient agreed to enrol in the study. No information about the individual patients will be required. This information will act as a denominator for calculation of percentage and proportions.

- Total number of procedure performed during the recruitment period
- Number of MRI procedures (enhanced and non-enhanced) performed during the recruitment period
- Categories/number of other procedure performed during the recruitment period

- **Centre Information (recorded once at the completion of recruitment):**

This information will be cumulative and consist of only numerical and will include all procedures performed by the investigator regardless of whether or not the patient agreed to enrol in the study. No information about the individual patients will be required. This information will act as a denominator for calculation of percentage and proportions.

- Total number of procedures performed during the recruitment period
- Categories/number of other procedure performed during the recruitment period

- Equipment for imaging (MRI, CT, ultrasound, X-ray machines, gamma camera, PET, fluoroscopy)
- Staffing of radiology department (optional)

Addition information will be recorded as categories or descriptive text (collected once at the end of recruitment period for a study centre/institution):

- Decision maker in the department – this information will be about the healthcare providers or administrator who play active role in decision making for the radiology department. For example: (categories) radiologist, head of department, cardiologist, managers, pharmacist (optional).
- Three challenges in the department in order of priority, reported as free text.

10.5 Appropriateness of Measurements

All assessments and measurements are appropriate and generally regarded as standard medical practice.

11 DATA HANDLING AND QUALITY ASSURANCE

11.1 Completing and Signing Case Report Forms

For eCRFs, data will be entered by trained site personnel with reasons given for any missing data. Any errors should be corrected within the electronic system. The audit trail will record all changes made, the date and time of the correction, and the person correcting the error. The appropriate electronic signature will be provided.

Any data recorded directly in the eCRF, for which no other written or electronic record will be maintained in the subject's medical record, will be considered source data and should be signed by the investigator(s) (e.g., results of physical examinations, vital signs testing, or the administration procedure).

11.2 Clinical Data Management

The Sponsor will be responsible for the processing and quality control of the data. Data management will be carried out by the Sponsor. The handling of data, including data quality control, will comply with all applicable regulatory guidelines.

The Stage 2 analysis (Section 10.2) will be performed at a later date and will not be part of the initial read out of the study. The images for the Stage 2 analysis will be selected and transferred via AGMednet to the Sponsor at the end of the recruitment period and will be archived for later use. Stage 2 blinded image evaluation results will be collected in a database that is separate from the database utilised for the Stage 1 analysis, and will not prohibit the procedures for locking and analysing the database for the Stage 1 analysis. No changes to the Stage 1 data will be made after the database is locked. Stage 1 and Stage 2 data will be merged after the blinded image evaluation is conducted for separate analysis.

11.3 Archiving

All study documentation at the investigator site and sponsor site will be archived in accordance with International Conference on Harmonisation (ICH) E6-Good Clinical Practice (GCP) and the CRO's quality standards and SOPs.

All study documentation at the investigator site and sponsor site will be archived for a minimum of 15 years following completion or discontinuation of the study, unless notified otherwise by the Sponsor or a longer period is required by local legislation. The investigator must request written agreement from the sponsor before destruction of archived study documentation.

12 STATISTICAL METHODS AND PLANNED ANALYSIS

The data will be analysed by the CRO. Any data analysis carried out independently by the investigator should be submitted to the sponsor before publication or presentation.

Data from participating centres in this protocol will be combined so that an adequate number of subjects will be available for analysis. The data will be summarised with respect to demographic and baseline characteristics, efficacy observations and measurements, safety observations and measurements.

12.1 General Statistical Considerations

Tabulations of summary statistics, graphical presentations, and statistical analyses will be performed using SAS[®] software, Version 9.3 or higher. Descriptive statistics for continuous data in summary tables will include the number of subjects in the analysis (n), mean, standard deviation, median, and range (minimum, maximum). Descriptive statistics for categorical data in summary tables will include counts and percentages. All data obtained on the eCRF and entered into the database will be provided in separate data listings showing individual subject values. The planning and reporting of statistical analysis will be carried out as described in the CRO's SOPs governing clinical studies.

12.2 Populations for Analysis

Full Analysis Set

The Full Analysis Set will include all enrolled patients who signed the informed consent.

Effectiveness Analysis Set

The Effectiveness Analysis Set will include all patients who received a GBCA and underwent an MR examination.

Safety Analysis Set

The Safety Analysis Set will consist of all patients who received GBCA during the study.

Investigator Analysis Set

The Investigator Analysis Set will include all investigators who performed at least one GBCA-enhanced MR procedure as part of this study.

Centre Analysis Set

The Centre Analysis Set will include all centres that were approved and initiated to take part in this study and performed at least one GBCA-enhanced MR procedure as part of this study.

12.3 Subject Demographics/Other Baseline Characteristics

A table will be provided with the following patient-level information:

- Number of subjects enrolled (full analysis set).
- Number of subjects included in the effectiveness analysis.
- Number of subjects included in the safety analysis.
- Number of subjects withdrawn from the study and the reason for withdrawal.

Demographic information (age, height, weight, and BMI) will be summarised using descriptive statistics. Gender and race will be summarised by counts and percentages.

Baseline characteristics such as the number of previous MR, SPECT, PET, special x-ray examinations (e.g., fluoroscopy, barium studies) and CT examination for current illness/disease, hepatic status, and renal status will be summarised.

Medical histories and concomitant medications will be summarised by counts and percentages.

12.4 Study Treatments

Study treatment will be administered according to clinical practice. The dose administered will be summarised by type and volume of GBCA as well as the volume of saline.

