The intravenous linear agents gadoxetic acid and gadobenic acid can continue to be used for liver scans because they are taken up in the liver and meet an important diagnostic need. In addition, gadopentetic acid given intra-articularly (into the joint) can continue to be used for joint scans because the dose of gadolinium used for joint injections is very low.

All other intravenous linear products (gadodiamide, gadopentetic acid and gadoversetamide) should be suspended in the EU.

Another class of gadolinium agents known as macrocyclic agents (gadobutrol, gadoteric acid and gadoteridol) are more stable and have a lower propensity to release gadolinium than linear agents. These products can continue to be used in their current

indications but in the lowest doses that enhance images sufficiently and only when unenhanced body scans are not suitable.

It is currently unknown and of high scientific interest with which dosages the radiologists use the gadolinium-containing contrast media still available on the market. Such information, which is very important for the referring physicians, can only be obtained by up-to-date observation and documentation in the daily routine.

It is also currently unknown and of further interest for the assessment of the applications, which criteria referrers consider for the administration of gadolinium-containing contrast agents after the publication of the EMA/457616/2017 requirements. In particular, it is unknown whether the presence of pre-existing renal insufficiency is taken into consideration, how often MR contrast agents are used in the same patient and whether this is dependent on indication and/or comorbidities. For example, this question is relevant to patients evaluated for multiple sclerosis and cancers, where it is unknown if notwithstanding the known brain retention of gadolinium, repeated contrast enhanced MR scans are considered necessary. Also, it is unknown if dose reductions, perhaps dependent on scanner magnetic field strength, are applied.

The study plan/protocol and the resulting documentation sheet of the requested study accurately collects data useful to clarify these points and will therefore provide more accurate insight into the potentially adapted clinical procedure.

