8.1.2 All GBCAs

Subjects will be administered a GBCA as part of clinical practice. All GBCAs will be selected by the sites and recorded as by the brand names.

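### Dose is to be summarised by GBCA type and volume without reference to body weight, so the planned summary cannot show whether doses are being reduced

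*Protocol*

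**What the plan says.** Protocol section 4 sets out the motivation. On dosage it says: "It is currently unknown and of high scientific interest with which dosages the radiologists use the gadolinium-containing contrast media still available on the market". On reductions it adds that "it is unknown if dose reductions, perhaps dependent on scanner magnetic field strength, are applied". It also asks whether pre-existing renal insufficiency is taken into account. It then says that the study plan and its documentation sheet "accurately collects data useful to clarify these points".

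Section 12.4 gives the whole of the planned dose analysis: "The dose administered will be summarised by type and volume of GBCA as well as the volume of saline". It names neither an amount in mmol nor an amount per kilogram.

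Three other places matter:

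- **Body weight.** Section 10.4.1: "Subject date of birth, gender, height, weight, and BMI (calculated) will be collected". Its only stated use is in section 12.3: "Demographic information (age, height, weight, and BMI) will be summarised using descriptive statistics".
- **Product.** Section 8.1.2: "All GBCAs will be selected by the sites and recorded as by the brand names".
- **Pattern of use.** The variables in section 10.1 and the patient-level summaries in section 12.5.3 cover what was imaged, in whom, why, on whose referral and whether it was repeated. Neither list includes dose.

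**The concern.** The stated question and the stated summary do not match. A question about dosages and dose reductions concerns how much agent is given relative to the patient's size. A volume in millilitres carries that information only if weight is held roughly constant. Section 7.2.3 admits patients of every age, so weight will vary widely, from children to heavy adults.

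Tabulating volume in one place and weight in another does not solve this. Two separate summaries say nothing about which volume went to which patient. A reader of the report could see that one product was given in smaller volumes and not know whether its users were reducing the dose or imaging lighter patients. Section 4 calls this question one of high scientific interest, and the planned tables would leave it open although the data to address it are in hand.

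**Working it through.** The plan states no dose figure, so there is nothing to reproduce. The check asks what a volume summary can and cannot reveal.

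**Inputs**

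- Concentration of Clariscan: 0.5 mmol/ml (section 8.1.1). Concentrations of other agents are not given.
- Volumes and body weights: assumed, for illustration only. They are not statements about correct dosing.

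**Formula**

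Amount per kg = volume (mL) × concentration (mmol/mL) / body weight (kg).

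**Step 1: one volume, different weights.** An assumed 15 mL at 0.5 mmol/mL is 15 × 0.5 = 7.5 mmol.

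| Assumed weight (kg) | Calculation | mmol/kg |
|---|---|---|
| 20 | 7.5 / 20 | 0.375 |
| 50 | 7.5 / 50 | 0.150 |
| 75 | 7.5 / 75 | 0.100 |
| 100 | 7.5 / 100 | 0.075 |
| 120 | 7.5 / 120 | 0.0625 |

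The same recorded volume spans a factor of 0.150 / 0.075 = 2 between 50 and 100 kg, and of 0.375 / 0.0625 = 6 between 20 and 120 kg.

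**Step 2: separate tables of volume and weight do not recover dose per kg.** Take two patients of 50 and 100 kg and two volumes, 10 and 20 mL, at 0.5 mmol/mL.

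- Larger volume to the heavier patient: 10 × 0.5 / 50 = 0.10 and 20 × 0.5 / 100 = 0.10 mmol/kg. There is no difference between the patients.
- Larger volume to the lighter patient: 20 × 0.5 / 50 = 0.20 and 10 × 0.5 / 100 = 0.05 mmol/kg. The difference is four-fold.

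The volume table and the weight table are identical in both cases, in mean, SD, median and range.

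**Step 3: adults only.** Assume weights are normal with mean 75 kg and SD 10 to 20 kg, limited to 35 to 150 kg, and that every patient receives 15 mL. Compared with the 75 kg patient's 0.100 mmol/kg, the simulated shares are:

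| SD of weight (kg) | More than 20% lower (below 0.08) | More than 20% higher (above 0.12) |
|---|---|---|
| 10 | 3% | 11% |
| 15 | 10% | 20% |
| 20 | 17% | 27% |

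A volume table would show 15 mL for everyone. With volume proportional to weight at 0.2 mL/kg, the mean volume is again about 0.2 × 75 = 15 mL, while the amount per kg is constant. The SD of volume would separate these two extremes (0 against 2.0 to 3.9 mL), but by Step 2 the spread does not identify dose per kg in general.

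**Step 4: concentration.** Within one product, concentration is constant, so volume converts to mmol by a fixed factor. Across products it need not be. At an assumed 1.0 mmol/mL, 15 mL in a 75 kg patient is 15 × 1.0 / 75 = 0.200 mmol/kg, against 0.100 at 0.5 mmol/mL. This affects only comparison or pooling across products.

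**The case against.** The strongest reply is that this is a matter for the SAP. Section 12.4 is two sentences long, it does not exclude a derived variable, and a protocol commonly leaves derivations and cross-tabulations to the SAP. Section 12.1 also promises listings of individual values, from which anyone could compute an amount per kilogram. Section 4 promises data, not a particular table, and for dose per kilogram the data will exist. This stands in part: nothing is lost, and an SAP could supply the measure. But section 12.4 is not silent. It chooses a measure, and the one chosen does not fit the question in section 4. Listings are not a summary.

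Four stronger readings are tempting and are not supported:

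- **That the study cannot answer the dosage question.** It can. Weight and brand are collected, and volume must be recorded for section 12.4 to be carried out.
- **That volumes of unlike concentration will be mixed.** Section 12.4 summarises by type as well as volume. If type means the individual product, the difficulty does not arise within it.
- **That a formal objective fails.** The objectives in section 5 are pattern of use, effectiveness and safety, and none of them names dose. The variables in section 10.1 agree with the summaries in section 12.5.3. No comparison of mean volume between agents or centres is planned, so no planned comparison is biased.
- **That field strength will not be recorded.** The protocol text names it only as an open question in section 4, but Table 2 includes unspecified procedure information and the eCRF is not shown.

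**Conclusion.** The point holds in a limited form. Section 4 says the study's data will help to clarify dosages and dose reductions. Section 12.4 plans a summary by type and volume that is not related to body weight, and that summary cannot distinguish a reduced dose from a lighter patient. The illustrated size is a two-fold range in mmol/kg behind one volume between 50 and 100 kg, and six-fold between 20 and 120 kg. It rests on assumed volumes and weights and on the stated Clariscan concentration; the true spread depends on how sites dose and whom they image, which the protocol does not give.

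This is a free improvement. It strengthens the answer to a descriptive question raised in the background, and changes no formal objective and no planned test. Renal status is in a similar position: section 10.4.2 collects it, section 12.3 summarises it at baseline, and nothing sets it against dose. Field strength is a question to settle rather than a demonstrated gap.

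**What to change.** In section 12.4, derive the amount per kilogram as volume × labelled concentration / body weight, and summarise it by individual GBCA with volume kept beside it. Add it to the patient-level list in section 12.5.3, with a breakdown by renal status.

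State in the protocol whether scanner field strength is a recorded procedure item. If it is, add that breakdown. If it is not, either add the field or withdraw the field-strength claim in section 4, because an amount per kilogram alone does not answer that part. This is best settled before enrolment, since an item not recorded prospectively may be hard to recover.

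The cost is one derived variable, a lookup of labelled concentrations by brand, one or two descriptive tables and at most one eCRF field. There is no extra burden on patients and no change to sample size. The change concerns reporting only and implies nothing about which dose should be used.
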